7.5.3.4. Testing

Sputum samples collected during the Screening Period and at designated time points during the study will be sent to the regional or central microbiological laboratory for mycobacterial culture, identification and quantification. Susceptibility testing and molecular testing (if applicable) of isolates will be performed at the central microbiological laboratory.

The time from receipt of sputum at the regional or central microbiological laboratory to a MAC-positive culture averages 3 weeks but may take up to 6 weeks. In addition, identification of MAC isolates to the species level using the line probe assay (LPA) or matrix-assisted laser desorption ionization-time of flight (MALDI-TOF) mass spectrometry, averages 1 to 3 days. Isolates that cannot be identified or speciated using LPA or MALDI-TOF will be identified and speciated via sequencing of the *rpoB* gene or 16S rRNA, which takes up to an additional 7 days.

Microbiological evaluation of sputum samples will include improvement in quantitative colony counts. Quantification of bacteria via colony counts on solid agar will be performed and assigned a categorical score similar to that reported by Griffith, et al. where colony counts were predictive of symptomatic and radiographic improvement ([Griffith, 2015](#)) (see [Table 1](#)). An improvement in quantitative culture counts will be defined as a reduction in ≥ 1 categorical score from the screening isolate and the previous month's categorical culture score.

Table 1: Categorical Scoring for Quantitative Culture Counts

Colonies (CFU/mL)	Categorical Culture Score ^a
No growth on agar or broth	0
Growth in broth only	1
1-49	2
50-99	3
100-199	4
200-299	5
≥300	6

Abbreviation: CFU = colony-forming units.

^a Categorical scores based on those reported in [Griffith, 2015](#).

The regional and/or central microbiological laboratory will follow standardized methods and procedures for MAC culture, identification, and susceptibility testing (following CLSI guidelines). All respiratory culture specimens will be cultured in appropriate liquid and solid media. If the results are negative on solid media, the liquid media will be held for 6 weeks before reporting the culture as negative.

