Phase 3: No data are available on symptom-based clinical response or minimal clinically important differences (MCIDs) using available PROs in patients with treatment-refractory MAC lung disease; therefore, previously published Month 6 sputum culture conversion rates in treatment-refractory MAC lung disease were used to initially estimate the number of patients expected to have an MCID improvement in PRO score, assuming a correlation between microbiological response and clinical symptom improvement. A Phase 3 study comparing ALIS + OBR versus OBR alone in patients with treatment-refractory MAC lung disease reported Month 6 sputum culture conversion rates of 29.0% compared with 8.9%, respectively, in the ITT population. Therefore, the initial sample size estimate for the Phase 3 part of the study assumes that the true number of patients experiencing an MCID improvement in PRO score is 30% for the epetraborole + OBR arm and 10% for the placebo + OBR arm. Assuming a 2:1 randomization and a 2-sided alpha of 0.05, a Phase 3 study of 186 patients with proven MAC lung disease (ie, in the Micro-ITT population) in the primary analysis (124 patients in the epetraborole + OBR arm and 62 patients in the placebo + OBR arm) would provide approximately 90% power, while also assuming when performing an analysis of proportions using the method of Miettinen and Nurminen. The total sample size for the Phase 3 part of the study is estimated to be 234 patients (156 patients in the epetraborole + OBR arm and 78 patients in the placebo + OBR arm) rather than 186 patients, to allow for approximately 20% of randomized patients to be excluded from the Micro-ITT Population due to lack of a study qualifying baseline culture (see Inclusion Criterion 3.a in Protocol Section 4.1); therefore, 186 patients are expected to be included in the Micro-ITT Population for the primary efficacy analysis. The sample size for Phase 3 will be reassessed after Phase 2 analyses, which will be based on data for all patients in Phase 2 through Month 6. Any needed sample size adjustment for Phase 3 will be determined by the Sponsor as part of the review of unblinded results from the fully independent Phase 2 data.

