2. Treatment: Epetraborole oral tablets 500 mg (two 250 mg oral tablets) QD + OBR or placebo oral tablets QD matched to epetraborole dosage + OBR
3. Variable: Sputum conversion rate is defined as proportion of patients having culture conversion based on 3 consecutive monthly negative sputum cultures for MAC by Month 6
4. Intercurrent events:
 - a. New, additional non-study-specific, antimycobacterial therapy that is potentially effective against MAC for reasons other than clinical failure of study drug: data collected after such therapy will not be used and patients will be classified as a failure for microbiological response (composite strategy)
 - b. Surgery for MAC lung disease for reasons other than clinical failure of study drug: data collected after such surgery will not be used and patients will be classified as a failure for microbiological response (composite strategy)
 - c. Permitted medications/interventions and or prohibited medications/interventions other than those described in bullets a and b: microbiological response data collected after permitted or other prohibited medications/interventions administration will be used as recorded (treatment policy strategy)
 - d. Inadequate compliance: patient data will be used as recorded (treatment policy strategy)

5. Population-level summary: Difference between epetraborole + OBR and placebo + OBR in sputum conversion rate by Month 6.

“Microbiological response” is defined as sputum culture conversion based on 3 consecutive monthly negative sputum cultures for MAC by Month 6. By-patient microbiological response will be presented for the Micro-ITT Population by Month 6. Descriptive statistics (n, %) will be presented by treatment group, along with the treatment difference (i.e. epetraborole + OBR response percentage minus placebo + OBR response percentage), associated 95% confidence interval and p-value, calculated using the method of Miettinen and Nurminen, both including (primary analysis) and excluding (sensitivity analysis) stratification by baseline ALIS use and the presence or absence of any fibrocavitary disease.

3.4.3.3 *Secondary Efficacy Endpoints*

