The secondary efficacy endpoints include microbiological response (by-patient sputum culture conversion monthly through Month 6 and by-patient microbiological improvement at Month 3 and Month 6), PRO symptom-based clinical response (mean changes in PRO domain scores or improvement of ≥ 1 grade in the key symptom with no worsening of other symptoms in the MACrO₂ PRO) monthly through Month 6, concordance of clinical response and microbiological response (concordance between PRO response and microbiological response), and rates of recurrence, reinfection, and relapse by Month 6.

“Microbiological response” is defined as sputum culture conversion based on 3 consecutive monthly negative sputum cultures for MAC by Month 6; “microbiological improvement” is defined as a decrease in MAC colony counts of ≥ 1 category from baseline. By-patient microbiological response at Months 6 and by-patient microbiological improvement by Month 3 and Month 6 will be presented for the Micro-ITT Population. Descriptive statistics (n, %) will be presented by visit and treatment group. Treatment difference, associated 95% confidence interval and p-value at Month 3 and 6, will be calculated using the method of Miettinen and Nurminen, both including (primary analysis) and excluding (sensitivity analysis) stratification by baseline use of ALIS and the presence or absence of any fibrocavitary disease.

By-patient microbiological improvement (decrease in MAC colony counts of ≥ 1 category from baseline) will be summarized using the categories of 0 = no growth on agar or broth; 1 = growth in broth only; 2 = 1 to 49 CFU/mL; 3 = 50 to 99 CFU/mL; 4 = 100 to 199 CFU/mL; 5 = 200 to 299 CFU/mL; 6 = ≥ 300 CFU/mL. If more than one sputum sample at the same visit is culture positive for the same species of MAC, the culture with the highest colony count will be used for determination of microbiological improvement.

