Clinical response as defined above for each individual PRO endpoint point (QOL-B respiratory domain, MACrO₂ original responder definition and response in total scaled score by threshold, SGRQ-C, NTM Symptoms Module, PGIS, CGIS, PGIC, and CGIC) will be presented dichotomously (Yes/No) for each treatment arm and will be presented as the treatment difference and associated 95% confidence interval and p-value, calculated using the method of Miettinen and Nurminen stratified by baseline use of ALIS and the presence or absence of any fibrocavitary disease for both the Micro-ITT and PP populations. In addition, to examine the influence of baseline severity on the treatment effect, clinical response rate by month will also be analyzed using a logistic regression model, including treatment and baseline key symptom severity (for MACrO₂ original responder definition only), baseline score (for QOL-B respiratory domain, MACrO₂ total scaled score, SGRQ-C Total Score, NTM Symptoms Domain), baseline severity in CGIS (for CGIS and CGIC), or baseline severity in PGIS (for PGIS and PGIC) as covariates. Stratification factors of baseline ALIS use and the presence or absence of any fibrocavitary disease will also be included as covariates in each model. For each logistic regression model, the estimated odds ratio and 95% confidence interval and corresponding p-value for the treatment effect will be presented.

Line plots of mean score (\pm SD) as well as mean (\pm SD) change from baseline in score over time will be produced for continuous PROs (e.g., QOL-B domain scores, MACrO₂ total scaled score, NTM symptom module score and total SGRQ-C score), with the two treatment groups indicated with different colors on the plot. A bar plot of categorical PROs (e.g., proportion of MACrO₂ responders, PGIS, PGIC, CGIS, CGIC and Meaningful Change Question) by treatment group will also be produced by visit.

In order to assess the concordance of PRO changes with microbiological changes the following summaries will be produced for each PRO. These will be produced at Month 3 and 6, as specifically noted below:

- Summary of PRO response (Response/Failure) versus sputum culture conversion (Conversion/No Conversion) by Month 6
- Summary of PRO response (Response/Failure) at Month 3 versus sputum culture conversion (Conversion/No Conversion) by Month 6

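### The Phase 3 culture-conversion and microbiological-improvement analyses leave out the measured baseline colony-count category; adding it is a cheap gain in precision, conditional on the category being prognostic

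*SAP*

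**What the plan says.** Outside the US, conversion by Month 6 is the primary endpoint and is tested first; in the US it is tested third (SAP 3.4). SAP 3.4.3.2 estimates it as a difference in rates by Miettinen-Nurminen, "both including (primary analysis) and excluding (sensitivity analysis) stratification by baseline ALIS use and the presence or absence of any fibrocavitary disease". SAP 3.4.3.3 applies the same method and the same two factors to microbiological improvement at Months 3 and 6, defined as a fall of at least one colony-count category from baseline. No Phase 3 analysis adjusts either endpoint for baseline colony count, and it is not among the subgroups in SAP 3.4.3.4.

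The variable is collected. Protocol 7.5.3.2 sends Screening sputum for quantification, and Protocol 7.5.3.4 states: "Quantification of bacteria via colony counts on solid agar will be performed and assigned a categorical score". Table 1 of that section runs from 0 to 6.

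The PRO endpoints are handled differently. The QOL-B ANCOVA in SAP 3.4.3.1 includes the baseline score. For the PRO responder endpoints SAP 3.4.3.3 says that "to examine the influence of baseline severity on the treatment effect, clinical response rate by month will also be analyzed using a logistic regression model", with the baseline score or severity and both stratification factors as covariates. No reason is given for the difference.

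**The concern.** Conversion and improvement have the same structure as the PRO responder endpoints: a binary outcome with a measured baseline value. A heavier initial load plausibly makes three consecutive negative months harder to reach. For improvement, the starting category determines which falls are possible. If the category is prognostic, leaving it out gives up precision and lets a chance difference in baseline load pass into the point estimate.

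This matters most for conversion. Failure on it outside the US blocks the tests of QOL-B and the MACrO₂ total score. SAP 1 records that the sponsor terminated the trial on 08 August 2024, so Phase 3 is likely to be smaller than planned.

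**Working it through.** **Inputs from SAP 2.2.7.** "Assuming a 2:1 randomization and a 2-sided alpha of 0.05"; the assumed response "is 30% for the epetraborole + OBR arm and 10% for the placebo + OBR arm"; "124 patients in the epetraborole + OBR arm and 62 patients in the placebo + OBR arm"; the design "would provide approximately 90% power".

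**Reproducing the plan's power.**
- Pooled rate = (124 × 0.30 + 62 × 0.10)/186 = 43.4/186 = 0.233.
- Null SE = √[0.233 × 0.767 × (1/124 + 1/62)] = 0.0658.
- Alternative SE = √(0.21/124 + 0.09/62) = 0.0561.
- Power = Φ[(0.20 − 1.96 × 0.0658)/0.0561] = Φ(1.267) = 89.7%.

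Exact enumeration of the unstratified Miettinen-Nurminen test gives 90.7%. The stated figure reproduces.

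**Cost of early stopping.** The documents do not give the Phase 3 Micro-ITT size. At assumed sizes, exact power is 83% (150 patients), 73% (120), 60% (90) and 40% (60).

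**What the category adds for conversion.** The fair comparator already holds both stratification factors. The simulation used 4,000 trials per cell with marginal rates held at 10% and 30%. Assumptions not in the documents are 35% ALIS use, 35% fibrocavitary disease, an odds ratio (OR) of 0.6 for each, and two baseline category distributions (spread and top-heavy). Both logistic score tests used the same simulated data. Power is in percent, spread / top-heavy:

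| N | OR per category | Strata only | Strata + category | Gain (points) |
|---|---|---|---|---|
| 186 | 1.0 | 90.4 / 91.1 | 90.4 / 90.8 | 0.0 / −0.3 |
| 186 | 0.85 | 90.1 / 90.6 | 90.9 / 90.8 | +0.8 / +0.2 |
| 186 | 0.7 | 91.0 / 90.7 | 92.9 / 92.2 | +1.9 / +1.5 |
| 186 | 0.5 | 90.5 / 91.0 | 95.4 / 96.4 | +4.9 / +5.4 |
| 120 | 0.7 | 74.1 / 73.5 | 77.3 / 76.3 | +3.2 / +2.8 |
| 120 | 0.5 | 72.8 / 73.2 | 81.8 / 83.6 | +9.0 / +10.4 |
| 90 | 1.0 | 61.1 / 60.1 | 61.0 / 60.0 | −0.1 / −0.1 |
| 90 | 0.7 | 61.1 / 60.6 | 63.5 / 63.6 | +2.4 / +3.0 |
| 90 | 0.5 | 59.0 / 60.3 | 67.7 / 70.4 | +8.7 / +10.1 |
| 60 | 0.7 | 41.9 / 43.6 | 44.0 / 46.9 | +2.1 / +3.3 |
| 60 | 0.5 | 42.4 / 41.2 | 50.8 / 50.6 | +8.4 / +9.4 |

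Monte Carlo error is about 0.5 to 0.8 points per cell. A second simulation, also with both strata in the model, gave about 0 points at OR 1.0, 2 to 3 at 0.7, and 3 (N = 186) to 9 (N = 90) at 0.5. For scale, across categories 2 to 6 an OR of 0.7 per category means about a 4-fold difference in odds (1/0.7⁴) and 0.5 means 16-fold (1/0.5⁴).

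**Extra Miettinen-Nurminen strata instead.** Adding the category as 2 or 3 further levels changes power at N = 186 by −1.0 to −1.4 points (OR 1.0), +0.1 to +0.8 (0.7) and +2.9 to +3.6 (0.5). At N = 60 and OR 0.7 it loses 0.5 to 3.7 points.

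**Chance imbalance.** Assume categories 2 to 6 with probabilities 0.25/0.15/0.15/0.15/0.30, for which the SD is about 1.6. With 60 versus 30 patients the SE of the difference in means is 1.6 × √(1/60 + 1/30) = 0.36. One trial in 20 would therefore have arms differing by at least 1.96 × 0.36 = 0.7 category. At OR 0.7 that shifts the log odds by 0.7 × 0.357 = 0.25. Around a 20% rate this is about 0.20 × 0.80 × 0.25 = 4 points, against a planned difference of 20.

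**Scoring conflict.** Protocol Table 1 and SAP 3.4.3.3 give broth-only growth category 1. SAP 3.1.4 treats broth growth without an agar count as missing, excludes such baseline patients from improvement denominators, and counts such post-baseline visits as non-response. Under one rule a fall from category 2 to broth-only growth is an improvement; under the other it is a failure.

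**The case against.** The strongest reply is that nothing in the plan is invalid. Randomization makes the stratified comparison unbiased, its type I error is controlled, and the confidence interval already reflects chance imbalance. Fibrocavitary stratification captures some disease severity. All of this stands, so the point concerns efficiency and robustness only.

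Several stronger readings are tempting but unsupported:

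- **That the plan certainly loses power.** Protocol 7.5.3.4 cites colony counts as predicting symptomatic and radiographic improvement, not conversion. If the category is not prognostic, nothing is lost.
- **That the gain is about 7 points at full size.** Cutting the variance by 1 − ρ² with ρ = 0.5 takes 89.7% to 96.6%. But no document supplies ρ, that calculation starts from an unadjusted test rather than the planned stratified one, and no cell at N = 186 in the table reaches such a gain.
- **That baseline is ignored for improvement.** The definition uses it; what is missing is adjustment for it. Low categories need not be less likely to improve either, since category 6 is open-ended (300 CFU/mL or more). No power calculation was done for this endpoint.
- **That a side-by-side presentation restores power.** It does not. Only the test named in the hierarchy has confirmatory power.
- **That a missing indicator keeps every patient.** It can for conversion. For improvement, a patient with no baseline category has no defined change. SAP 3.1.4 expects some such samples, and their share is not given.

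Two further cautions stand. The 30% versus 10% scenario is a planning assumption, and SAP 1 reports that epetraborole was not superior on conversion in Phase 2. At 60 versus 30 patients those rates give only about 3 placebo converters (0.10 × 30), which is sparse for a model with several covariates.

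**Conclusion.** The point holds as a low-cost improvement, not as a flaw in validity. Both microbiological endpoints omit a baseline value that the trial scores, while the PRO responder endpoints are adjusted for theirs. For conversion the gain ranges from nothing to about 3 to 5 points of power at the planned 186 patients, and to about 9 to 10 at an assumed 90. The upper ends require a 16-fold difference in odds across categories 2 to 6. A moderate association gives about 2 to 3 points. The logistic adjustment cost essentially nothing even when the category had no effect.

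The loss from early stopping is much larger: 90.7% to 60% at 90 patients, about 31 points. Adjustment would recover at most a third of that (10/31). These figures rest on the assumed Phase 3 size, category distribution and prognostic strength, none of which the documents give.

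**What to change.** Before Phase 3 unblinding, amend SAP 3.4.3.2 and 3.4.3.3 as follows.

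1. Fit a logistic model with treatment, baseline colony category as a linear score, ALIS use and fibrocavitary disease. Average each patient's predicted probability under treatment and under placebo over the analysed Micro-ITT patients, and report the difference. This targets the same difference in rates as the estimand. Do so for conversion by Month 6 and improvement at Months 3 and 6.
2. State whether this is supportive or replaces stratified Miettinen-Nurminen as the hierarchy test for conversion. Confirmatory power rises only in the second case. The Phase 2 data, already unblinded and separate from Phase 3, could show how prognostic the category is before the choice is made.
3. Do not add colony category as further Miettinen-Nurminen strata.
4. Reconcile SAP 3.1.4 with SAP 3.4.3.3 and Protocol Table 1 on broth-only growth. For any baseline category still missing, use a missing indicator for conversion only.
5. Specify penalized fitting if converters are few.

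The cost is SAP wording and a variant of a model already planned for the PRO responders, plus the missing-baseline and sparse-event rules. No new data are needed. If Phase 3 is already unblinded, the analysis belongs in a post hoc addendum or the CSR, labelled as such, as SAP 1 provides.

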1 INTRODUCTION

This Statistical Analysis Plan (SAP) provides a description of the statistical methods to be implemented for the analysis of data from Study EBO-301 (Protocol Version 5.0, dated 07 June 2023), entitled “A Phase 2/3, Randomized, Double-Blind, Placebo-controlled, Multicenter, Prospective Study to Assess the Efficacy, Safety, and Pharmacokinetics of Orally Administered Epetraborole in Patients with Treatment-refractory *Mycobacterium avium* Complex Lung Disease (MACrO₂),” which was intended as a single study to support registration. EBO-301 was designed as a seamless trial randomizing patients to either treatment with epetraborole plus an optimized background regimen (OBR) or placebo plus an OBR, with no pause between Phase 2 and Phase 3 enrollment. Phase 2 enrollment was completed in September 2023 (n=80), at which time enrollment in the Phase 3 part of the trial started immediately.

On 08 August 2024, the Sponsor terminated the trial based on topline, unblinded results from the Phase 2 part of the study and notified the Agency accordingly. The Phase 2 study met its primary objective of demonstrating the ability to validate the MACrO₂ PRO and showed a preliminary efficacy signal favoring epetraborole based on a responder analysis (39.5% [15/38] epetraborole vs 25% [10/40] placebo, p=0.19). However, the epetraborole plus OBR arm was not superior to the placebo plus OBR arm in sputum culture conversion rate. Nonetheless, the Sponsor is continuing with an analysis of the Phase 3 study data because of the positive Phase 2 clinical efficacy data noted.

This SAP supports the planned analyses of the primary, secondary, and exploratory efficacy and safety endpoints identified for evaluation both in the United States (US) by the Food and Drug Administration (FDA) as well as for other regulatory agencies outside the US. In accordance with the above protocol, any primary or secondary objectives or endpoints and hierarchical testing procedures that differ between regions will be specifically designated by “in the US” for FDA regulatory interpretation or “outside the US” for other regulatory agency interpretation in this document.

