2.2 Study Design

2.2.1 Overview

Refer to Protocol Section 3.1 Summary of Study Design for full details of the study overview.

Briefly, this is a pivotal Phase 2/3, double-blind, placebo-controlled study of eptraborole + OBR versus placebo + OBR in patients with treatment-refractory MAC lung disease. This study will enroll adult patients with treatment-refractory MAC lung disease who meet all eligibility criteria.

This study features a sequential Phase 2/3 approach with an initial Phase 2 assessment of clinical responses (based on clinical symptoms and/or functional assessments), microbiological responses, safety, and PK associated with oral eptraborole, prior to the superiority analysis of oral eptraborole versus placebo in the Phase 3 part of the study.

In both the Phase 2 and Phase 3 parts of the study, each patient will complete multiple PRO measures including MACrO₂, QOL-B, NTM Symptoms Module, SGRQ-C, and global patient and clinician assessment scales (Patient Global Impression of Severity [PGIS], Patient Global Impression of Change [PGIC], Clinician Global Impression of Severity [CGIS], Clinician Global Impression of Change [CGIC]), and Meaningful Change Question (to be answered after each completion of the PGIC). An electronic PRO system will be used during the study to allow patients to complete the study questionnaires electronically.

The MACrO₂ PRO will be completed twice before the first dose of study drug to assess test-retest reliability (within 1 to 2 weeks prior to randomization, and on randomization day prior to study drug administration) and once weekly for the first 6 months of the study; other PROs and global assessment scales will be completed at baseline and once monthly for the first 6 months of the study. The QOL-B, NTM Symptoms Module, SGRQ-C, and PGIS will also be completed during Screening for test-retest reliability assessment. The PGIC, CGIC, and Meaningful Change Question will not be completed at baseline. After Month 6, all PROs will be completed every 3 months (84 days \pm 7 days), at End of Therapy (EOT), and at Late Follow Up (LFU). Sputum samples for microbiological assessments will be collected during the Screening period, once monthly for the first 6 months of the study, and then every 3 months (84 days \pm 7 days), at EOT, and at LFU.

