in QOL-B respiratory domain score of ≥ 8 based on a minimally clinically important difference (MCID) established for bronchiectasis patients ([Quittner 2015b](#)), as well as by a threshold (11.1 points) determined as part of a blinded anchor-based psychometric analysis of the observed QOL-B respiratory domain scores from Phase 2 patients across pooled treatment arms and visits as a potentially more specific indicator of meaningful improvement in treatment-refractory MAC patients. Similarly, response in MACrO₂ total scaled score is defined as an improvement (decrease in total score) by a threshold (11.3 points) determined as part of a blinded anchor-based psychometric analysis of the observed total scaled scores from Phase 2 patients across pooled treatment arms and visits as an indicator of holistic symptom-based improvement in treatment-refractory MAC patients. Response in SGRQ-C total score is defined as an improvement in SGRQ-C total score of ≥ 4 based on a MCID established for COPD patients ([Jones 2023](#)). A corresponding threshold for a response endpoint in the NTM Symptoms domain of the NTM Module has not been defined, as an MCID has yet to be clearly established for this endpoint, but this study will investigate distribution-based minimal important differences (MIDs) using $0.5 \times$ baseline SD and the standard error of the mean (SEM) of the baseline measurement, where in both cases baseline is pooled across both treatment groups in the Micro-ITT Population, as experimental response thresholds. Response in PGIS or CGIS at each post-baseline visit is defined as a reduction in severity of one or more grades relative to baseline. Response in PGIC or CGIC at each post-baseline visit is defined as a reported change of severity category of “Much Better” or “A Little Better.” For all of the above PRO response definitions, missing results at the given timepoint will be considered failures in the Micro-ITT analysis.

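### One of the two experimental NTM Symptoms response thresholds is a standard error of the mean, which is not a within-patient change threshold

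*SAP*

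**What the plan says.** SAP 3.4.3.3 explains that no response threshold exists for the NTM Symptoms domain because no minimal clinically important difference has been established. Instead, "this study will investigate distribution-based minimal important differences (MIDs) using" two quantities: 0.5 × the baseline SD, and "the standard error of the mean (SEM) of the baseline measurement". The sample is also specified: "where in both cases baseline is pooled across both treatment groups in the Micro-ITT Population". Both are to serve "as experimental response thresholds". SAP 3.4.1.3 has the same text for Phase 2.

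NTM Symptoms response then enters the stratified Miettinen–Nurminen comparison (difference, confidence interval and p-value, Micro-ITT and PP) and a logistic regression adjusted for baseline score. The concordance tables against culture conversion and colony counts are to be produced for each PRO.

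Test-retest data on this score are planned. SAP 2.2.1 states: "The QOL-B, NTM Symptoms Module, SGRQ-C, and PGIS will also be completed during Screening for test-retest reliability assessment". Protocol 7.5.5 places the two completions at Day −14 to −7 and on Day 1 before dosing.

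**The concern.** A distribution-based minimal important difference asks whether one patient's change exceeds what the instrument's noise would produce. The quantity for that purpose is the standard error of measurement, SD × √(1 − reliability). The SAP spells out the standard error of the mean, which shares the abbreviation SEM but equals SD/√n. It says how precisely a group average is known, carries no information about an individual's change, and tends to zero as the sample grows.

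A programmer following the text would compute the wrong statistic. A label that nearly half of unchanged patients could earn would then be reported as a minimal important difference and cross-tabulated as response against microbiology. The cut-off would also depend on how many patients happened to be enrolled.

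**Working it through.** **Inputs from the documents**
- Planned Phase 3 n: "186 patients are expected to be included in the Micro-ITT Population for the primary efficacy analysis" (SAP 2.2.7).
- Phase 2 n: 38 + 40 = 78, from "39.5% [15/38] epetraborole vs 25% [10/40] placebo" (SAP 1).
- Actual Phase 3 n: not given. Because "the Sponsor terminated the trial based on topline, unblinded results from the Phase 2 part of the study", it may be below 186.
- Score: 0–100, higher is better, 4-point items (Protocol 7.5.5.3). The number of items in the domain is not in the text available.

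**Assumed inputs (not in the documents)**
- Baseline SD 15, 20 or 25.
- Test-retest reliability r of 0.7, 0.8 or 0.9.

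**The plan's own figure.** The SAP gives no numerical NTM threshold. The only stated figure used here is n = 186. With 62 vs 124 patients, 10% vs 30% and two-sided 0.05, a normal approximation gives power 0.897, in line with the stated 90% or so. Also 186/(1 − 0.20) = 232.5, rounded up to 233, against the stated 234. The planned n is reproduced.

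**Step 1: ratio of the two candidates.** (SD/√n) / (0.5 SD) = 2/√n, so SD cancels.
- n = 78: 2/8.83 = 0.23.
- n = 186: 2/13.64 = 0.15.

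**Step 2: size in points.**

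| SD | SD/√78 | SD/√186 | 0.5 SD | SD√(1 − r), r = 0.7 / 0.8 / 0.9 |
|---|---|---|---|---|
| 15 | 1.70 | 1.10 | 7.5 | 8.22 / 6.71 / 4.74 |
| 20 | 2.26 | 1.47 | 10.0 | 10.95 / 8.94 / 6.32 |
| 25 | 2.83 | 1.83 | 12.5 | 13.69 / 11.18 / 7.91 |

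The written cut-off is 1.1–2.8 points. If early termination left n at 40–60, it would be 1.9–3.95. For comparison, the same section sets 8 and 11.1 points for the QOL-B respiratory domain, 11.3 for the MACrO₂ total scaled score and 4 for the SGRQ-C; these are different instruments, so the comparison is only of order of magnitude.

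**Step 3: unchanged patients labelled responders.** With no true change, the observed change has SD equal to SD × √(2(1 − r)). The share at or above a cut-off c is 1 − Φ(c / (SD√(2(1 − r)))). SD cancels for all three cut-offs.

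| Cut-off | r = 0.7 | r = 0.8 | r = 0.9 |
|---|---|---|---|
| SD/√n, n = 186 | 46.2% | 45.4% | 43.5% |
| SD/√n, n = 78 | 44.2% | 42.9% | 40.0% |
| 0.5 SD | 25.9% | 21.5% | 13.2% |
| Standard error of measurement | 24.0% | 24.0% | 24.0% |

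The last row is 1 − Φ(1/√2) for any r.

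**Step 4: how far the figures move.** At n = 40–60 the written rule gives 36–43%. If the score is a simple mean of k items scored 0–3, it moves in steps of 100/(3k). With 4 to 12 items assumed and a half-step correction, the written rule gives about 27–47%, lowest with few items and high reliability.

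**Step 5: does the low cut-off weaken the treatment comparison?** Take SD 20, r = 0.8 and an assumed uniform 5-point benefit. The SD of change is 20√0.4 = 12.65.
- Cut-off 1.47: 45.4% vs 61.0%, difference 15.6 points.
- Cut-off 8.94: 24.0% vs 37.8%, difference 13.8 points.

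Divided by √(p(1 − p)), with p the response rate pooled at 2:1, these are 0.31 and 0.29. On this model the low cut-off does not reduce the ability to see a difference.

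**The case against.** **Little rests on this threshold.** It is one of two candidates that the SAP itself calls experimental, and half an SD is reported alongside it. NTM Symptoms is outside the three-endpoint hierarchy in SAP 3.4, which says no claims are intended for other secondary endpoints. The domain's ANCOVA and MMRM use no cut-off, and the Phase 3 time-to-response analyses do not include it. All of this stands and limits the point to interpretation.

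**The points and percentages are not document facts.** SD, reliability and the actual Phase 3 n are all missing. This stands: they are an illustration. The 2/√n ratio needs only n.

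**The score is stepped.** At SD 20, with up to 14 items (step 100/42 = 2.38), cut-offs of 1.47 and 2.26 both mean at least one step. The operating rule could then be identical in both phases. This stands for complete questionnaires, so the dependence on n is a flaw in the definition that may have little practical effect.

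**Intent is inferred.** The documents do not say that the standard error of measurement was meant. The use as a minimal important difference and the planned test-retest data make it likely. Either way, the statistic written is unsuitable.

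**A stronger reading.** A reader might infer that the treatment difference is diluted, or that a main trial conclusion is at risk. The documents do not support either. Step 5 goes the other way under a uniform benefit; dilution could arise if only a subgroup benefits, but nothing in the documents shows that.

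**Conclusion.** The point holds as a definitional error in one of two exploratory cut-offs, written the same way for both phases. The standard error of the mean is not a within-patient change threshold. It is 23% of the companion threshold at n = 78 and 15% at n = 186, a result that needs no assumed SD. The figures of 1.1–2.8 points and 40–46% depend on the assumed SD, reliability, n and continuous normal score, and they move as Step 4 shows. What suffers is the meaning of response in the NTM Symptoms responder and concordance tables. It is worth correcting because it is plain on the page and cheap to mend.

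**What to change.** In SAP 3.4.3.3, replace the second candidate with: standard error of measurement = baseline SD × √(1 − ICC), with the ICC from the Screening (Day −14 to −7) and Day 1 NTM Symptoms scores, pooled across arms. Compute the number from pooled Phase 2 data and state it before Phase 3 is unblinded, in line with the 11.1- and 11.3-point thresholds already taken from pooled Phase 2 data. The half-SD candidate can stay as it is.

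Leave 3.4.1.3 unedited. SAP 1 limits changes after Version 2.0 to Phase 3, and rewriting a Phase 2 responder rule after unblinding would be post hoc. Record the correction in the CSR as a documented deviation.

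The cost is one sentence and no new data. There is a small downside: the ICC assumes patients are stable between the two completions, which may fail for those who restart their background regimen at Screening (Protocol 4.1, criterion 3.d). The corrected rule would still label 24% of unchanged patients as responders under the normal model, so it remains an experimental threshold.
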